## 12. SAFETY

Unless otherwise stated all summaries will have corresponding listings.

The summaries will be according to the actual treatment received; any deviation from the treatment received will be listed.

### 12.1. Treatment and Study Duration

- 1) Duration of treatment will be summarized descriptively; separately for each study drug [ALIS/ELC, AZI, ETH] and for all study drugs combined.

$$\text{duration of treatment (days)} = \text{date of last dose} - \text{date of first dose} + 1$$

This definition does not account for protocol-allowed interruptions.

- 2) Study drug exposure will be summarized descriptively; separately for each study drug [ALIS/ELC, AZI, ETH] and for all study drugs combined.

$$\begin{aligned} \text{duration of exposure (days)} = \\ \text{date of last dose} - \text{date of first dose} + 1 - \text{total number of days with protocol-} \\ \text{prescribed prescribe interruptions due to safety reasons} \end{aligned}$$

For all study drugs combined the derivation is

$$\begin{aligned} \text{duration of exposure (days)} = \\ \text{date of last day all study drugs are concurrently administered} - \\ \text{date of first day all study drugs are concurrently administered} + 1 - \\ \text{total number of days any study drug was interrupted due to safety reasons} \end{aligned}$$

- 3) The duration of study will be calculated as number of days between randomization and end of study and summarized descriptively.

$$\text{duration of study (days)} = \text{end of study date} - \text{date of randomization} + 1$$

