4.2. Discontinuation of Study Drugs and Participant Discontinuation/Withdrawal

4.2.1. Discontinuation of Study Drugs

All subjects are encouraged to stay in the study for continued safety monitoring regardless of discontinuation of study drugs. If a subject discontinues one or more study drugs (ALIS/ELC, AZI, and/or ETH), they will remain on the other study drug(s) and continue with the scheduled study visits. For these subjects, it is highly encouraged to stop all MAC treatment at Month 6 (per study design) to evaluate the primary and secondary endpoints during the off treatment period. However, if deemed medically necessary per the Investigator, these subjects who prematurely discontinue one or more study drugs may be allowed to continue treatment during the off treatment period.

If a subject discontinues ALIS or ELC:

- The reason for ALIS or ELC discontinuation will be recorded in eCRF.
- The subject will remain on the other study drugs (AZI and ETH) and continue with the next scheduled study visit.
- At the next scheduled visit, the subject will complete the EOT visit assessments.
- The subject will complete a Month 6 visit when they reach Month 6.

If a subject discontinues AZI and/or ETH, the reason for drug discontinuation should be recorded in the eCRF. The EOT visit should not be completed at this time. The subject will remain on the other study drugs (ALIS/ELC and AZI or ETH) and should initiate therapy consistent with the 2020 ATS/ERS/ESCMID/IDSA treatment guidelines ([Daley et al., 2020](#)), and continue with the next scheduled study visit. Any changes to therapy and treatment regimen should aim to prevent the development of macrolide resistance. Changes to treatment should be discussed with the Medical Monitor to ensure compliance with the 2020 ATS/ERS/ESCMID/IDSA treatment guidelines.

For subjects who discontinue one or more study drugs, replacement therapy may be provided at the discretion of the Investigator; this is not considered rescue therapy.

Subjects may be discontinued from one or more study drugs at the discretion of the Investigator if they meet treatment stopping criteria per local labeling guidance.

If a subject withdraws consent from continued safety monitoring, the EOS visit should be completed.

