5.1.4.1. Dose Interruption

It is recommended that all subjects remain on prescribed daily treatment throughout the study. However, experience has shown that dose interruptions may be helpful to avoid discontinuation of ALIS (Swenson et al., 2020). If a subject experiences a nonserious AE that is distressing and an interruption of study drugs dosing (ALIS/ELC, AZI and/or ETH per Investigator discretion) is needed to avoid discontinuation of study drugs, contacting the Medical Monitor to discuss subject management is encouraged.

At the discretion of the Investigator, dose adjustments of azithromycin and/or ethambutol may be allowed if criteria are met per local label recommendation (ie, renal or hepatic insufficiency).

All dose interruptions must be documented in the subject's source documentation and recorded in the eCRF.

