### Treatment Period

The treatment period starts with the first dose of ALIS/ELC, AZI and/or ETH.

The end of treatment (EOT) is defined as the date of the last dose of ALIS/ELC, AZI and/or ETH whichever study drug dose is taken last.

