### 7.4.5. Missing Dates Drug Interruption

Missing end date of drug interruption will be imputed by date of EOT or EOS whichever comes first.

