### 12.3. Dose Interruption

Dose interruptions will be recorded in the subject's diary and eCRF. All dose interruptions reported are protocol-allowed interruptions due to safety reasons. Number and percent of subjects who interrupted study drug(s) will be presented.

Basic summaries of length of interruption (days) will be presented for each interruption. Dose interruption due to COVID-19 will be summarized and listed.

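### SAP 12.1: the combined-drug exposure formula subtracts safety-interruption days that fall outside the concurrent-treatment window, so some subjects can get an exposure that is too short or negative

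*SAP*

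**What the plan says.** SAP 12.1 (Treatment and Study Duration) defines exposure separately for ALIS/ELC, AZI and ETH, and once more for all study drugs combined. The combined version has three parts:

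- end of the window: "date of last day all study drugs are concurrently administered";
- start of the window: "date of first day all study drugs are concurrently administered", with 1 added to the difference;
- amount subtracted: "total number of days any study drug was interrupted due to safety reasons".

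Three other places decide which days can enter the subtraction.

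- Protocol 4.2.1 says of a subject who stops ALIS or ELC: "The subject will remain on the other study drugs (AZI and ETH) and continue with the next scheduled study visit". It likewise keeps a subject on the remaining study drugs when AZI or ETH is stopped.
- Protocol 5.1.4.1 lets the investigator interrupt ALIS/ELC, AZI and ETH singly or together, and requires every interruption to be recorded in the eCRF.
- SAP 12.3 states: "All dose interruptions reported are protocol-allowed interruptions due to safety reasons". Every recorded interruption therefore qualifies.

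The SAP's Treatment Period text (Section 4.2) ends treatment at the "date of the last dose of ALIS/ELC, AZI and/or ETH whichever study drug dose is taken last". Recorded treatment can thus run well past the day on which the first drug was stopped.

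**The concern.** The two halves of the formula cover different periods. The first half stops at the last day on which all drugs are taken together. The second half counts interruptions of any drug at any time. An AZI or ETH interruption after ALIS/ELC has been stopped lies outside the first half but is still deducted from it. The same happens if AZI or ETH is the drug stopped first. It needs no missing or imputed dates.

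The per-drug formula directly above does not have this problem when dates are complete, because a drug's own interruptions normally lie between its own first and last dose. That built-in limit is lost once one drug sets the window and the interruption belongs to another.

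At stake is the combined summary that is meant to show time on the full regimen net of interruptions. Protocol 10.7.1 asks for exposure by treatment group, for each medication and in total as randomized. With about 50 subjects per arm, a few understated or negative values would show up in the minima and listings and could move the means.

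**Working it through.** The documents give no figure for this quantity, so there is nothing to reproduce. The check applies the formula as written to day counts, then repeats it counting only interruption days inside the window. All subject histories are hypothetical: the documents give no interruption frequencies or lengths and no expected stopping days. Day 1 is taken as the first concurrent day, and 6 months as 6 x 28 = 168 days, using the 28-day month in SAP 7.6.1.

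Formulas:

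- As written: E = (last concurrent day - first concurrent day + 1) - all safety-interruption days of any drug.
- Window-limited: E* = the same span - safety-interruption days inside the span.
- Error: E* - E = interruption days after the last concurrent day.

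| Hypothetical history | As written (E) | Window-limited (E*) | Error |
|---|---|---|---|
| ALIS stopped after Day 60; ETH interrupted Days 90-130 (130 - 90 + 1 = 41 days) | 60 - 41 = 19 | 60 | 41 |
| ALIS stopped after Day 30; same ETH interruption | 30 - 41 = -11 | 30 | 41 |
| ALIS stopped after Day 84; ALIS interrupted Days 40-46 (7 days), ETH Days 100-113 (14 days) | 84 - 21 = 63 | 84 - 7 = 77 | 14 |
| ALIS stopped after Day 30; no interruption | 30 | 30 | 0 |
| All drugs to Day 168; ALIS interrupted Days 40-46 | 168 - 7 = 161 | 161 | 0 |

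In the first row the value is 41/60 = 68% too low for that one invented subject. The last two rows show that neither early stopping alone nor an interruption inside the window causes an error.

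**When a negative value is possible.** Suppose the remaining drugs run to Day 168 with a dose on that day, and the concurrent window is W days with no interruption inside it. At most 167 - W interruption days can follow the window. E is then at worst W - (167 - W) = 2W - 167, which is below zero for W of 83 or less (83 - 84 = -1). This is an arithmetic bound, not an expected value.

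**Overlapping interruptions.** The text does not say outright whether a day on which two drugs are interrupted counts once or twice. With ALIS stopped after Day 30 and both AZI and ETH interrupted on Days 60-73 (14 days), the formula as written gives 30 - 14 = 16 or 30 - 28 = 2. The window-limited value is 30 under either count.

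**The case against.** The strongest reply is that a first-to-last concurrent window with interruptions subtracted is most naturally meant to remove only interruptions within that window, and that a programmer may well code it so. That is plausible as intent, but nothing in either document says it. The term is a total over any study drug, and followed literally it returns a wrong number from complete dates.

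Several limits on the importance of the point do stand.

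- A reader might infer that every subject who stops ALIS early is miscalculated. That is not so: at least one recorded interruption day after the last concurrent day is needed.
- The summary is not the only source of information. In the first two examples the separate ALIS/ELC exposure line gives the correct 60 and 30 days. It would not replace the combined figure where another drug is interrupted inside the window. Listings accompany the safety summaries, so a negative value would be visible; one that is merely too short would be harder to spot.
- A reader might also infer that the error falls mainly on the ALIS arm, because Protocol 9.9.6 reports that most ALIS-treated subjects in an earlier refractory-disease study had their first adverse event within 60 days. That statement concerns the timing of first events. It gives no discontinuation rate and nothing on later AZI or ETH interruptions in either arm, so it does not support a claim of imbalance.
- Counting each day once is arguably already the ordinary reading of the term. Stating it is a small added safeguard.

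**Conclusion.** The concern holds in a limited form. As written, the combined-exposure formula gives a wrong value for any subject who permanently stops one study drug, continues the others, and has a recorded safety interruption after the last concurrent day. The value is too short by exactly the number of interruption days after that day, and it is negative when the subtracted days exceed the length of the window. How many subjects would be affected cannot be estimated from the documents, and the worked cases show the mechanism only.

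The consequence is minor. The quantity is a descriptive safety summary. Per-drug exposure does not contain the cross-drug term, the time at risk for treatment-emergent adverse events (SAP 12.4) is built from dose and end-of-study dates, and neither compliance nor the efficacy analyses use combined exposure. No study conclusion depends on it. It is still worth correcting, because the rule is stated and yields impossible values from valid data.

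**What to change.** In SAP 12.1, replace the last term of the combined formula with: number of calendar days between the first and the last day of concurrent administration (inclusive) on which at least one study drug was interrupted for safety reasons, each calendar day counted once.

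This removes the possibility of negative values and settles the overlap question. It also keeps interruption end dates imputed under SAP 7.4.5 from carrying days beyond the window into the combined figure. The cost is one sentence in the SAP and one line of derivation code. Data collection, study conduct and treatment do not change.

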### 12.2. Compliance

Subjects will be required to bring all their used and unused study drug supplies to in-clinic study visits during the treatment period or, if the visit is being conducted virtually, have all used and unused study drug supplies available for accountability review.

Compliance will be categorized (>120%, 80-120%, <80%) and tabulated (number and percentage of subjects).

$$\text{Compliance (\%)} = 100\% \times \text{Number of units used} / \text{number of expected units}$$

where the unit for all study drugs is 'mg'.

Number of units used will be derived using the data from the form "Drug Accountability".

The expected number of units is the sum of all expected daily units from the first dose of the respective study drug reported on form "Prior and Concomitant Medications" until the last dose of the study drug reported on form "End of Treatment".

**Protocol-allowed dose interruptions** due to safety reasons are reported on eCRF form "Prescribed Dose Interruptions"; consequently, for the purpose of compliance calculations the number of expected units during these interruptions is 0.

**Protocol-allowed dose adjustments** will be reported on the form "Prior and Concomitant Medications" and can be identified by the product code "INVESTIGATIONAL DRUG". The prescribed dose in the reported interval is the dose (mg) reported on the form. A dose adjustment is protocol-allowed if the "Reason for treatment" is "Adverse event". If the dose frequency is adjusted to a value different to 'once daily', then the daily dose must be derived.

ETH tablets are available in doses of 100 mg and 400 mg. Tablets are combined to match a daily dose of 15 mg/kg. The **expected per-protocol dose of ETH** is the first dose reported on the form "Prior and Concomitant Medication" dose for each subject is the dose reported at the date of first dose on form "Prior and Concomitant Medications".

**Table 6: Expected Daily Doses of Study Drugs**

Study Drug	Interval	Expected Per-protocol Dose (mg/day)
ALIS/ELC	Protocol-allowed dose interruption due to safety reason	0
	Protocol-allowed dose adjustment due to safety reasons	as reported in EDC form CM
	Other *	590
AZI	Protocol-allowed dose interruption due to safety reason	0
	Protocol-allowed dose adjustment due to safety reasons	as reported in EDC form CM
	Other *	250
ETH	Protocol-allowed dose interruption due to safety reason	0
	Protocol-allowed dose adjustment due to safety reasons	as reported in EDC form CM
	Other *	dose at the day of first ETH dose on EDC form CM

\* 'Other' is every day between First Dose (from CM) and Last Dose (from EOT) which is not in the 2 above mentioned intervals (Protocol-allowed dose interruption due to safety reason, Protocol-allowed dose adjustment due to safety reasons)

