1.5. Treatment, Route, Dosage, Treatment Period

Eligible subjects with non-cavitary lung disease with new (initial or subsequent) MAC lung infections who have not started treatment for their current infection (see [Section 4](#)) and who have signed the ICFs will be randomized and will receive treatment as follows (see [Figure 1](#))

- ALIS 590 mg QD + AZI 250 mg QD + ETH 15 mg/kg QD for 6 months, or
- ELC (matching placebo for ALIS) + AZI 250 mg QD + ETH 15 mg/kg QD for 6 months

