5.1.4. Study Drugs Administration

ALIS 590 mg or ELC will be administered QD by inhalation via nebulization over approximately 6 minutes to up to 15 minutes. Written directions for preparing and administering ALIS or ELC will be provided to subjects. On the day of study visits, ALIS or ELC administration will be the last procedure to be conducted (see Table 4).

Azithromycin 250 mg tablets dosed 1 tablet QD, and ethambutol tablets dosed at 15 mg/kg will be taken by mouth QD, with or without food. The Investigator should refer to local labeling guidance:

- To monitor AZI and ETH use
- To conduct any necessary monitoring procedures (eg, ECG monitoring, ophthalmic exams, audiology testing)

The Investigator is responsible for recording any AEs and SAEs as appropriate (see Section 9.10).

Timing of Administration

Study drugs should be administered QD around the same time each day, any time of day, in the fasted or as-fed condition.

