#### **8.5. COVID-19 Impact**

Potential COVID-19 impact is captured in the eCRF and will be summarized by subject.

Subject disposition summary and listing will include:

- Screen failure related to COVID-19
- Treatment discontinuation related to COVID-19
- Early termination of study related to COVID-19

AE overview table and listings will include:

- AEs that fall into the category of COVID-19 related

Summary table and listing of dose interruption will include:

- Dose interruption related to COVID-19

Summary and listing of protocol deviations will include:

- Protocol deviations due to COVID-19

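### SAP compliance rules treat any adverse-event-coded dose adjustment, including of ALIS/ELC, as protocol-allowed, while the protocol provides adjustment for azithromycin and ethambutol only, on label criteria

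*SAP*

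**What the plan says.** **Protocol.** Section 5.1.4 states that "ALIS 590 mg or ELC will be administered QD by inhalation via nebulization". Section 5.1.4.1 covers two kinds of change:

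- Interruption may apply to any of the three drugs, where "an interruption of study drugs dosing (ALIS/ELC, AZI and/or ETH per Investigator discretion) is needed to avoid discontinuation of study drugs".
- Adjustment is narrower: "dose adjustments of azithromycin and/or ethambutol may be allowed if criteria are met per local label recommendation (ie, renal or hepatic insufficiency". ALIS/ELC is not named.

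Section 5.1.5 sets the non-compliance limits at below 80% and above 120%, exempting interruptions that the investigator instructs for safety. It also says that accountability review takes account of prescribed interruptions and adjustments, without naming a drug.

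**SAP.** Section 12.2 defines compliance as mg used over mg expected, in the classes <80%, 80-120% and >120%. It has its own test for adjustments: "A dose adjustment is protocol-allowed if the" reason recorded on the medication form is an adverse event. The test is not limited by drug and has no label criterion. The expected dose is then the recorded dose, and a changed frequency is converted to a daily dose. Table 6 carries a row "Protocol-allowed dose adjustment due to safety reasons" for ALIS/ELC, AZI and ETH alike. Days outside an allowed interruption or adjustment are scored against 590 mg (ALIS/ELC), 250 mg (AZI) or the first recorded ETH dose.

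On interruptions, SAP 12.3 states: "All dose interruptions reported are protocol-allowed interruptions due to safety reasons". SAP 8.5 plans a separate summary of "Dose interruption related to COVID-19".

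SAP Table 9, the list of changes from the protocol, contains only the end-of-treatment definition.

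**The concern.** The SAP calls an adjustment protocol-allowed on a test that the protocol does not contain. This can move subjects across the 80% line in two ways:

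1. An ALIS/ELC reduction coded to an adverse event lowers the denominator to the reduced dose, although the protocol describes no ALIS/ELC adjustment.
2. An AZI or ETH adjustment that meets the protocol's label criterion, but carries another reason code, keeps the full-dose denominator.

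At stake is how the compliance table is read. Readers use it to judge whether the randomized inhaled drug was taken. Protocol 10.7.1 plans a count of doses received for each drug, but SAP 12.1 lists durations only. The compliance table is therefore the only planned SAP summary built on mg taken, and another table would not reveal a reduced intake scored as 100%.

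**Working it through.** The documents give no compliance figure to reproduce, so the check applies the SAP 12.2 formula to illustrative subjects. The reduced doses and dates are assumptions chosen to show the arithmetic; they are not proposed regimens.

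**Inputs**

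- Regimen: "ALIS 590 mg QD + AZI 250 mg QD + ETH 15 mg/kg QD for 6 months" (protocol 1.5).
- 28 days per month (SAP 7.6.1), so 6 × 28 = 168 days.
- Compliance = 100 × mg used / sum of expected daily mg (SAP 12.2).
- Class boundary of interest: 80% (protocol 5.1.5, SAP 12.2).

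**ALIS/ELC, half the daily mg from Day 29, reason coded as an adverse event, recorded dose taken**

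- Used: 28 × 590 + 140 × 295 = 16,520 + 41,300 = 57,820 mg.
- Expected under the Table 6 adjustment row: 57,820 mg. Compliance 100%, class 80-120%.
- Expected at 590 mg daily: 168 × 590 = 99,120 mg. Compliance 57,820 / 99,120 = 58.3%, class <80%.
- With 180 days instead of 168: 61,360 / 106,200 = 57.8%.
- With the reduction from Day 1 of 168: 49,560 / 99,120 = 50.0%.

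In a 50-subject arm, each subject classified differently moves the class percentage by 1/50 = 2 points.

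**AZI, half the daily mg from Day 29 on a label criterion, reason not coded as an adverse event**

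- Used: 28 × 250 + 140 × 125 = 24,500 mg.
- Expected under the SAP (full dose): 168 × 250 = 42,000 mg. Compliance 58.3%, class <80%.
- If the adjustment counted as allowed: 100%.

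**ETH, 900 mg reduced to 500 mg, same coding** (900 mg is 15 mg/kg for an assumed 60 kg)

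- From Day 29: (28 × 900 + 140 × 500) / (168 × 900) = 95,200 / 151,200 = 63.0%.
- From the midpoint: (84 × 900 + 84 × 500) / 151,200 = 117,600 / 151,200 = 77.8%.
- A lower dose already in place at the first ETH dose is itself the expected dose, so it reads 100% and is not affected.

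**How large a reduction crosses 80%?** If a fraction r of the full dose is taken on a share f of days, compliance against the full dose is 1 − f(1 − r). This is below 0.80 when f > 0.20 / (1 − r).

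| Dose reduction | r | Share of days needed to fall below 80% |
|---|---|---|
| 50% | 0.50 | more than 40% |
| 25% | 0.75 | more than 80% |
| 20% | 0.80 | never |

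Only reductions that are substantial and long-lasting change class.

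**The case against.** **Adherence is properly measured against what was prescribed, and protocol 5.1.5 says that adjustments are taken into account.** This is a fair defence of prescribed dose as a denominator. But that sentence names no drug and does not extend 5.1.4.1, which does. Nor does the SAP's rule that it prevails over the protocol (SAP 2) settle the matter, because the label in Table 6 refers back to the protocol.

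**The 100% is not automatic.** A reader might infer that any recorded ALIS/ELC reduction becomes the expected dose, or that used and expected always agree. Neither is so. The reason must be an adverse event; otherwise 590 mg applies. Used mg come from drug accountability and expected mg from the medication form, so they agree only if the recorded dose is taken.

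**The AZI/ETH side is narrow.** Protocol 9.9.2 requires clinically significant laboratory abnormalities, or those needing intervention, to be recorded as adverse events, and 9.9.3 lists renal impairment among events of special interest. New renal or hepatic insufficiency would usually carry the adverse-event reason and pass the SAP test. What remains is mainly adjustment for a pre-existing condition, or under another code.

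**Interruptions.** A reader might infer that COVID-19 interruptions are always given zero expected units. SAP 12.2 and Table 6 already limit zero units to safety reasons, and protocol 6.3 has COVID-19 infection reported as an adverse event, so such an interruption can be a safety one. The sentence in SAP 12.3 is loose rather than a clear conflict. It still needs tightening, because protocol 6.3 also foresees loss of access to the product.

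**Bias between arms.** Protocol 9.9.6 links ALIS to respiratory adverse events, so a reader might infer that ALIS compliance will be overstated relative to ELC. The documents neither report nor predict dose adjustments by arm, so this is not supported.

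**Conclusion.** The contradiction stands and is undeclared. Protocol 5.1.4.1 and SAP 12.2 with Table 6 differ both on which drugs may be adjusted and on which reasons qualify. Followed as written, the SAP can score an adverse-event-coded ALIS/ELC reduction at 100% where the same intake is 58.3% of 590 mg daily. It can also score a label-based AZI or later ETH change at 58.3% or 63.0% where the adjusted dose was taken in full. These sizes rest on the assumed doses, dates and reason codes above; the documents give no basis for how often such cases occur.

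The adjustment rule feeds only a descriptive table. The SAP defines no per-protocol set (SAP 6), and compliance class enters no endpoint or imputation rule (SAP 9.3.1.2.1 and 9.3.2.2.1). A reader might infer that efficacy results are at risk; they are not. This review takes no position on which dosing rule is right.

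**What to change.** 1. Reconcile protocol 5.1.4.1 with SAP 12.2 on which drugs and which recorded reasons make an adjustment protocol-allowed, or declare the difference in SAP Table 9.
2. Align the expected-dose rows of Table 6 with the reconciled rule.
3. Reword SAP 12.3 so that only interruptions with a recorded safety reason receive zero expected units, as SAP 12.2 and Table 6 already imply.
4. Optionally, tabulate compliance a second time against the randomized regimen. This is a different quantity, closer to dose intensity, and is not needed to remove the contradiction.

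The cost is a small rewording of the SAP, plus one column if item 4 is adopted. Depending on how the rule is reconciled, reported ALIS/ELC compliance may become less favourable.
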